Study Overview: This is a randomized, double-blind inpatient or outpatient human laboratory study. Procedures will be completed as a 7-day inpatient protocol in AUD subjects (N=75) and a 4-day outpatient protocol in an age and gender-matched comparison group of healthy control

(HC) subjects (N=75). On day 1, AUD subjects will be administered an alcohol beverage to control time from last drink before undergoing the first fMRI session. Two hours after alcohol administration, resting-state and alcohol-cued activity will be measured. Following the fMRI session on day 1, all subjects will be randomized to once-daily MIFE or placebo administration. They will also complete cognitive assessment tasks such as the Wisconsin Card Sorting Task (WCST) and two parts of the Wechsler Adult Intelligence Scale-III (WAIS-III), the digit span and the digit symbol substitution tests. They will receive their first medication dose on day 1. Over the next 3 days, AUD participants are monitored as they go through supervised alcohol withdrawal. On day 4, all subjects will complete a second fMRI session to quantify FC changes as a function of alcohol withdrawal and medication administration across key brain regions recently shown to be under GR regulatory control. They will also repeat cognitive assessment tasks. On day 5, AUD subjects complete the Trier Social Stress Test (TSST) followed by the Alcohol Motivated Response (AMR) procedure, during which subjects work for either their preferred alcohol beverage or money. On day 6, AUD subjects will participate in a cumulative alcohol administration procedure during which subjective and physiological responses to alcohol are repeatedly assessed. AUD subjects are discharged on day 7 after completion of the cognitive assessment tasks and a brief intervention. AUD participants are followed for two weeks post discharge. HC participants are followed for one week post second fMRI.

Table 1. Study Day	AUD Procedures	HC Procedures
Pre-admission	Assessment, Medical History, Vital Signs, blood work	Assessment, Medical History, Vital Signs, blood work
Day 1	Updated assessment, blood work, urine pregnancy test; alcohol administration and fMRI session 1 MIFE/placebo randomization and dosing; Cognitive Assessment	Updated assessment, blood work, urine pregnancy test; fMRI session 1 MIFE/placebo randomization and dosing; Cognitive Assessment
CRU stay	Days 2-6: Alcohol withdrawal monitoring	
MIFE/placebo dosing	Days 2-6	Days 2-4

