MIFE has a rapid onset of action and achieves peak plasma levels within 1 - 2 hrs of oral dosing. Peak plasma levels and bioavailability increase as a function of dose but are not directly proportional to dose. However, plasma concentrations of MIFE metabolites do increase in direct proportion to dose; metabolites have antiglucocorticoid activity and contribute to long-acting drug effects (Pomara et al., 2002). MIFE is effective with once-a-day dosing. The half-life is 40 hrs following a single dose and 84.6 hrs following multiple doses. Following discontinuation of MIFE, plasma levels are detectable for up to 2 weeks (Heikinheimo et al., 2003). For this study, we selected to use the high MIFE dose of 1200mg, based on recent clinical trials for other neuropsychiatric disorders associated with HPA-axis dysfunction, and that 1200 mg MIFE has been safely administered over extended periods (MIFE Investigator Brochure, Corcept Therapeutics). This study only exposes subjects to MIFE for up to 6 days. We are not planning to reduce MIFE dose during such a brief treatment period. If a subject experiences significant medication side-effects or any serious adverse event or if the participant declines to continue medication, then we will discontinue that participant from the study. It

should be noted that inpatient subjects are under continuous nursing observation throughout the CRU stay and thus adverse events can be identified and addressed rapidly. HC subjects will be instructed to call the study doctor if they have any adverse events. Subjects will be randomized to active MIFE and placebo on a 2:1 ratio.

In the proposed study, MIFE will be administered under an IND ([name] 124365). MIFE (300 mg) and matching placebo will be provided by Corcept Therapeutics, Menlo Park, CA. We will overencapsulate the medication and placebo as necessary. The Johns Hopkins Bayview Investigational Drug Services (IDS) will maintain the inventory and dispense the medication. MIFE absorption and elimination are not affected by age, body weight, BMI, race or sex (Mifepristone Investigator Brochure, Corcept Therapeutics).

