Since MIFE has potent antiprogestational effects, women participants will undergo a urine pregnancy test at the time of the initial alcohol sensitivity and prior to the first MIFE dose. On day 1, participants will be dosed after the fMRI session under nursing observation. On all subsequent days, inpatient participants will be dosed once daily at 9 am under nursing observation and HC outpatient participants will be given take home medication and asked to take the medication under nursing observation via video teleconference. Blood draws for MIFE trough and peak plasma level determinations will be drawn at 15 minutes before dosing and 90 minutes after dosing, respectively. MIFE blood draws will be completed for outpatient HC participants on day 4 only. Subjects can discontinue taking study medication at any time, ending study participation. Discontinued subjects will be asked to complete post-discharge follow up.

fMRI scans for functional connectivity and alcohol cue activation on Days 1 and 4: Both AUD and HC participants undergo fMRI sessions. On day 1, all subjects report to the IPSAR office at 9 am, complete interim assessment procedures, urine drug and pregnancy screens and receive a calorie-controlled breakfast. AUD and HC smokers with tobacco use disorder (TUD) will receive a nicotine patch (21mg). At 10 am on day 1 only, AUD subjects will receive an alcohol drink in a standardized calorie-free mixer targeting a blood alcohol level of 80mg% based on gender and BMI. We have included this drink for several reasons. Most importantly, we want to standardize time from last drink to start of scanning across AUD subjects, since subjects will come for admission with varying abstinence durations. Secondly, we want to minimize the impact of both alcohol intoxication and withdrawal on this initial scan, and so have attempted to time the scan to begin when BAL is at or near 0mg%. Finally, we anticipate that this pre-scan drink will act as a primer for the alcohol cuing procedure employed in the study. At 1 pm, all subjects undergo rs-FC and CA fMRI procedures.

fMRI Scanning procedures: All studies will be conducted at 3T in the F.M.Kirby Research Center for Functional Brain Imaging. We will follow all COVID-related safety procedures implemented by the Kirby Research Center. We will counter-balance for handedness and always use the right hand for responses.

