In this cumulative alcohol dosing procedure, placebo and three active alcohol drinks are administered at timed intervals to increase BAL progressively (0, 0.03, 0.067, 0.10%) during a single session. Alcohol doses for each subject are determined using a Computerized Blood Alcohol Calculator (CBAC©) which adjusts for age, height and gender differences in body water and duration of drink consumption. This allows us to target similar BALs in males and females. Investigational Drug Services prepares each 120 mL drink by mixing the appropriate mL of 95% ethanol and a non-caloric sweetened beverage using a w/v metric. The placebo drink is blinded by floating 1 mL of ethanol on top of the beverage and by placing an ethanol-soaked wristband around the glass to deliver a strong alcohol odor. Active alcohol drinks are prepared in the same manner. Subjects are monitored continuously by staff, who also ensure consumption of each drink is paced over 10 min. Staff will physically distance from the participant during alcohol consumption when participants will have to remove their masks.

Subjects complete a computerized battery of subjective assessments at baseline before alcohol consumption (-45 minutes) and every 45-min thereafter. The battery requires 10 minutes for completion and includes the (1) Drug Effect Visual Analog Scale (VAS) (Uhart et al., 2013) , (2) Brief Craving Scale (Cox et al., 2001), (3) Biphasic Alcohol Effects Scale (BAES) (Martin et al., 1993), (4) Subjective High Assessment Scale (SHAS) (Schuckit, 1980), (5) POMS (D. M. McNair et al., 1992; D. McNair and Heuchert, 2003) Tension Anxiety subscale. At time 0, the placebo drink is administered. Active alcohol drinks are administered at 45 min intervals

(+45, +90 and +135). Breath alcohol levels are determined at baseline (-15) and 15 min after consumption of each drink. Heart rate, skin conductance and skin temperature are recorded continuously using a noninvasive monitor; blood pressure is recorded every 5 min. Participants also complete a brief battery of psychomotor/reaction time tasks to measure level of intoxication.

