As shown in Figure 1, cumulative alcohol dosing procedures generate highly reproducible BALs and subjective effects, with little between-subject variability. Subjective effects track BAL across the ascending and descending limb of the curve. Using this procedure, we have shown that the GABRA2 gene influenced alcohol subjective and physiological effects (Uhart et al., 2013). To date, we have completed this procedure over 150 subjects.

[figure not shown]

Figure 1. Time course of BAL and self-rated effects on the VAS and SHAS. Arrows indicate times of placebo

(P) and each alcohol drink (A1, A2, A3) consumed.

Discharge and Follow-up:

AUD subjects are discharged on day 7 following cognitive assessment and participation in a brief motivational intervention for alcohol use; information on treatment availability will be provided prior to discharge from the CRU. Under the supervision of [name], the intervention is delivered by Master's-level staff following procedures outlined in NIAAA Clinician Guide to Brief Intervention.

All female participants are advised to use nonhormonal birth control (e.g., condoms) for the duration of a one month period following discharge. All male participants will also be advised to use condoms for the duration of the follow-up visits and for at least 5 half-lives of the drug plus 90-days after the last dose of mifepristone. All subjects will be given a supply of condoms.

AUD subjects return weekly for 2 follow-up visits. HC subjects return one week post-second fMRI for a follow-up visit. As described above, MIFE is a long acting compound; plasma levels will likely remain elevated throughout the first two weeks post-discharge at the time of the follow-up visits. At each follow-up visit, participants provide self-reported alcohol use using TLFB procedures for the period since they were last seen, complete self-report measures of alcohol craving (as listed under the inpatient stay), medication side effects (SAFTEE) and adverse events. In addition, we will obtain a blood spot for PEth determination as a biomarker of recent drinking intensity. We also will get a blood sample for MIFE level and, at week 1 follow-up, a sample will be obtained to test for potassium level. Subjects will be reminded of the importance of use of nonhormonal birth control and/or condoms and will be provided with condoms.

b. Study duration and number of study visits required of research participants.

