- c. Justification and safety information if non-FDA approved drugs without an IND will be administered.

During the alcohol sensitivity session, subjects will drink 3 doses of alcohol intended to bring their terminal BrAL to 0.10 mg/dL. Also, at the conclusion of the AMR session, participants can consume up to 5 standard drinks of their preferred alcohol type/brand, based on the number of alcohol reinforcers earned during the session. Beverages containing more than 7% alcohol are not regulated by the FDA; they are regulated by the Bureau of Alcohol, Tobacco, Firearms and Explosives. These beverages are legally sold to adults.

7. Study Statistics

- a. Primary outcome variables:

- adverse events and side-effects;

- fMRI changes in re-FC and CA across brain regions under GR regulatory control;
- Reduction in TSST-induced alcohol motivation and drinking;
- cardiovascular responses (HR, BP, ECG) during alcohol sensitivity sessions;
- alcohol euphoric and sedating effects during sensitivity sessions using VAS and Adjective Scales.

b. Secondary outcome variables will examine the effects of MIFE on a variety of psychological measures during alcohol abstinence, alcohol sensitivity sessions and outpatient visits. Secondary outcome measures include:

- Craving for alcohol during the inpatient stay, assessed using VAS, PACS, OCDS, and AUQ;
- Alcohol withdrawal symptom severity, assessed using the CIWA-Ar;
- Mood and personality assessments during the inpatient stay (BPRS, BDI, and BAI);
- Alcohol use during the outpatient follow-up, assessed using timeline followback self-report and PEth levels.

c. Statistical plan including sample size justification and interim data analysis.

Primary and secondary outcome variables will undergo data cleansing and Corrective/Preventive Measures based confirmation of accuracy and missing data. We will perform exploratory data analyses initially (stem-leaf displays, box plots, histograms, and Q-Q plots) and, if necessary, appropriate data transformations will be performed.

Power analyses: All power estimates are based on type I error =0.05, Power > 0.8. Specific aims are to compare GR antagonism versus placebo for:

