Aim 2. Reduction of alcohol withdrawal symptoms and craving, and improvement in low mood during early alcohol abstinence. Power for this aim was based on Vendruscolo et al (2015) (Fig 2A) in which MIFE effects were examined on VAS craving scores. Our hypotheses test if placebo (size = n) is different from MIFE. Comparing placebo effects (mean=11.5 (SD=2.1) to active drug effects (mean=9.3 (SD=2.2), total sample size required for the proposed aim is 39 (i.e.,20 in each group).

Aim 3. Reduction of stress-induced alcohol motivation and drinking. Power for this aim was based on Vendruscolo et al (2015) (Fig 2B) in which MIFE effects were examined on drinking during an outpatient treatment phase of the study. This calculation is based on between-subject calculation which overestimates the sample size requirement. Comparing placebo effects (mean (SEM) = 38.0 (10.2)) to active drug effects (mean (SD) = 27.5 (10.2)), total sample size required is 32. Using data from our AMR session in which mean number of drinks is 4.33 (sd = 3.17), we are powered to observe a 50% or greater reduction in drinks earned within the session.

Aim 4. Reduction of alcohol reward and sensitivity. Based on our preliminary data (4A1, Aim 3) and a sample of 50 GR antagonist vs 25 placebo subjects, we are powered to detect a difference of 3.0 degrees (3.3%) in peak skin temperature. Further, using data from our current alcohol sensitivity procedure (mean peak VAS total=168 (SD=118); mean peak liking=47.9 (SD=36.9)), we are powered to observe a 45 - 50% or greater reduction in alcohol subjective effects.

Aim 5. Side-effects. Power calculation is based on the assumption that the number of side-effect reports and adverse events follows a Poisson distribution. In preliminary data (Concept Investigator Brochure), an average of 12 events was reported in MIFE treated subjects. We estimate that 22 subjects in each group will give power > 0.8 for this statistical test.

Statistical Analyses: For aims 1 – 4, AUD and HC subjects will be separately grouped.

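### AUD subjects drink alcohol on day 1 before randomisation, but no response is recorded, so the primary day 6 alcohol-response comparison has no pre-drug measure of response to adjust for

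*Combined protocol and SAP*

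**What the plan says.** - **Day 1 drink (section 4a, fMRI scans on Days 1 and 4).** At 10 am "AUD subjects will receive an alcohol drink in a standardized calorie-free mixer targeting a blood alcohol level of 80mg" per cent, and scanning starts at 1 pm. Three reasons are given: to standardise time since last drink, to scan with blood alcohol near zero, and to prime the cue task. No response scale, heart rate or skin temperature reading is scheduled after the drink.
- **Order of events (section 4a, Study Overview).** "Following the fMRI session on day 1, all subjects will be randomized to once-daily MIFE or placebo administration".
- **Day 6 (section 4a, Alcohol Sensitivity Session).** The response scales and continuous physiology are described only here. Of the scales, the text says "The battery requires 10 minutes for completion". The pre-drink reading comes 45 minutes before the first drink, after dosing that began on day 1.
- **Outcome status (section 7a).** Cardiovascular responses and euphoric and sedating effects in the sensitivity session are both listed as primary.
- **Power (section 7c).** "All power estimates are based on type I error =0.05, Power > 0.8". Aim 4 uses "a sample of 50 GR antagonist vs 25 placebo subjects" and "mean peak VAS total=168 (SD=118); mean peak liking=47.9 (SD=36.9", and claims power for a reduction of 45 to 50% or more. Section 4a, MIFE Administration, confirms the allocation: "Subjects will be randomized to active MIFE and placebo on a 2:1 ratio".
- **Analysis (section 7c, Aim 4).** Unspecified baseline measures are to be examined as confounders and enter the model only where judged necessary.

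**The concern.** Aim 4 compares arms between subjects in one session, held on drug. How strongly a person responds to alcohol before treatment is the natural predictor of how strongly that person responds on day 6. The design already creates the occasion to measure it: a common target dose, given to every AUD subject before allocation. The day 6 pre-drink reading is no substitute, because it is taken on drug and before any alcohol.

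At stake is precision. Person-to-person spread goes straight into the error term of a primary outcome. The plan describes the procedure as one in which "cumulative alcohol dosing procedures generate highly reproducible BALs and subjective effects, with little between-subject variability", yet the SDs it uses for Aim 4 power are most of the size of the means. The power statement for the same outcome also looks optimistic for the planned allocation, so there is little margin.

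**Working it through.** **Inputs.** From section 7c: mean 168, SD 118 (peak VAS total); mean 47.9, SD 36.9 (peak liking); 50 active versus 25 placebo; alpha 0.05; power above 0.8. Sidedness is not stated. From section 5: over 90% of subjects complete. The correlation r between day 1 and day 6 responses is not in the documents, so it is an assumption, shown as a range.

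**1. Spread.** 118/168 = 70%; 36.9/47.9 = 77%.

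**2. The plan's own figure.** Detectable reduction (normal approximation) = (1.960 + 0.842) × √(1/n₁ + 1/n₂) × SD/mean.
- 1:1 split of 75: 2.802 × √(2/37.5) = 0.647, giving 0.647 × 0.702 = 45.4% and 0.647 × 0.770 = 49.8%. This matches the stated 45 to 50%.
- Planned 50 versus 25: 2.802 × √(1/50 + 1/25) = 0.686, giving 48.2% and 52.9%.

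**3. The same with the noncentral t.** The detectable standardised difference at 50 versus 25, two-sided, is 0.695.

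| Setting | VAS total | Liking |
|---|---|---|
| 1:1 split of 75, two-sided | 46.1% | 50.5% |
| 50 vs 25, two-sided | 48.8% | 53.6% |
| 45 vs 22.5 (10% loss), two-sided | 51.6% | 56.6% |
| 50 vs 25, one-sided | 43.2% | 47.4% |

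At 50 versus 25, two-sided, power is 73% (VAS total) and 65% (liking) for a 45% reduction, and 82% and 74% for a 50% reduction.

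**4. Which sidedness?** Aim 3 gives a hint. Its difference is 38.0 − 27.5 = 10.5. Taking 10.2 as the SD, 16 per group has 80.4% power in a two-sided 1:1 t-test, and this reproduces the stated total of 32. Two-sided is therefore the likelier reading for Aim 4 too.

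**5. Effect of a day 1 covariate.** Residual SD = SD × √(1 − r²), with one degree of freedom lost; equivalent AUD sample = 75/(1 − r²). 50 versus 25, two-sided:

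| Assumed r | SD factor | Power at 45% (VAS / liking) | Detectable at 80% (VAS / liking) | Equivalent N |
|---|---|---|---|---|
| 0.3 | 0.954 | 77% / 69% | 46.6% / 51.1% | 82 |
| 0.4 | 0.917 | 80% / 73% | 44.8% / 49.1% | 89 |
| 0.5 | 0.866 | 85% / 78% | 42.3% / 46.4% | 100 |
| 0.6 | 0.800 | 90% / 84% | 39.1% / 42.9% | 117 |

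**The case against.** **The randomised comparison is valid as it stands.** This is correct. A reader might infer that, without a pre-drug session, Aim 4 is biased or cannot show a reduction. The documents do not support that: Hypothesis 4a is framed against placebo, and randomisation supports that contrast.

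**The missing covariate does not explain the power shortfall.** Also correct. That link is tempting, but section 7c computes power from unadjusted means and SDs, so no covariate was assumed. The gap arises from allocation: the stated range fits 1:1 and the plan is 2:1.

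**The shortfall is not uniform.** VAS total reaches 82% power at a 50% reduction with all 75 subjects, and a one-sided test would meet the stated range for both measures. The figures above also assume equal SDs. If the active arm's SD shrank in proportion to its mean, power at a 45% reduction would be about 85% (VAS total) and 78% (liking), by the normal approximation. The claim is therefore one of under-specification and a likely shortfall.

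**The gain rests on an assumed r, which may be modest.** One drink to 80 mg% differs from cumulative dosing to 0.10%. Day 6 follows withdrawal and possible drinking on day 5, and a single change score is used to predict a session peak. This stands.

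**Other pre-drug covariates exist.** Drinking history, AUDIT, PEth and sex are known before dosing, and craving is rated in the scanner after the day 1 drink. None measures response to alcohol. The MIFE Administration text mentions an initial alcohol sensitivity, but the schedule has one such session, on day 6.

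**Extra ratings before scan 1 would fall on AUD subjects only.** True, and not balanced against HC. It is minor: only AUD subjects get the drink already, and the cue task itself asks for craving ratings after every block.

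**The low-variability remark cannot be refuted outright.** It introduces a figure that is not shown, and deleting it would change no result.

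**Conclusion.** The point holds as a missed opportunity for precision. The day 1 drink precedes randomisation, its effect is not measured, and a primary comparison with SDs of 70% and 77% of the mean has no pre-drug measure of alcohol response to adjust for. The benefit is uncertain. At r = 0.3, power for a 45% reduction rises only from 73% to 77% (VAS total) and from 65% to 69% (liking); at r = 0.5 it reaches 85% and 78%.

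A separate finding concerns the power statement. Under a two-sided test with equal SDs at 50 versus 25, liking misses 80% power across the whole stated range and VAS total misses it at the lower end. With 10% loss, both detectable reductions exceed 50%. Heart rate and blood pressure have no power figure, and the skin temperature figure comes without an SD, so neither could be checked.

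**What to change.** 1. **Section 4a, day 1.** Have AUD subjects complete the Drug Effect VAS, BAES and SHAS, with heart rate and skin temperature recorded, before the existing drink and at one fixed time after it, well ahead of the scan. The drink itself does not change. The Study Overview puts measurement two hours after alcohol, while the fMRI section has the drink at 10 am and scanning at 1 pm; reconcile these before fixing the time.
2. **Section 7c, Aim 4 analysis.** Prespecify the day 1 change (post-drink minus pre-drink) as a fixed covariate for the matching day 6 outcome, in place of the discretionary baseline adjustment.
3. **Section 7c, Aim 4 power.** Restate the detectable reductions at 2:1, giving sidedness and expected attrition.

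**Cost.** Two batteries of about 10 minutes with instruments already in use, two physiological recordings, and a short change to the analysis text. If r proves to be near zero, the covariate costs one degree of freedom. The downside is possible slight priming before scan 1 in AUD subjects only: balanced between MIFE and placebo, because allocation comes later, but not between AUD and HC.
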